### 3.2 Trial Design

The trials are randomized, open-label, comparative trials. The trials duration for the individual subjects will be approximately 9 weeks (including a 28 days screening period) and each subject will attend 8 visits. Subjects with IDA will be stratified according to type of underlying disease (women with IDA due to gynaecological blood losses; yes/no) and screening s-phosphate level (< 3.5 mg/dL or  $\geq$  3.5 mg/dL), and randomized 1:1 to one treatment course of one of the following treatments:

- Group A: iron isomaltoside (1000 mg infusion at baseline, cumulative dose: 1000 mg)
- Group B: ferric carboxymaltose (750 mg infusion at baseline and day 7, cumulative dose: 1500 mg)

It is intended that 50 % of the recruited subjects are women with IDA due to gynaecological blood losses.

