### 3.3 Subject included

#### 3.3.1 Sample Size Determination

Data from a previous trial conducted with iron isomaltoside 1000 mg suggests that the incidence of hypophosphatemia in a gynaecology population with/without heavy uterine bleeding can be expected to be approximately 10 % (P-Monofer-IDA-01, 1000 mg; n=3/29=10.3 %, 95 % Confidence Interval (CI) = 2-27 %, gynaecology subgroup; n = 1/10 = 10.0 %, 95 % CI = 0-45 %). For ferric carboxymaltose, the incidence has been observed to be 40-70 % (e.g. Wolf *et al.*, 2013; n = 10/17 = 59 %, 95 % CI = 33-82 %). The significance level is set to 5 %, and the power is set to 80 %. Assuming incidences of 15 % for iron isomaltoside and 40 % for ferric carboxymaltose, 49 subjects in each treatment group is required to detect a difference between the treatment groups.

To account for the uncertainty, and to gain more safety information, 60 subjects per treatment group will be randomized in both trials.

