### 7.2 Analysis and Presentation of the Secondary Safety Endpoints

The secondary safety endpoints are the following:

- Incidence of *s*-phosphate < 1.0 mg/dL at any time from baseline to day 35
- Time with hypophosphatemia (i.e. time with *s*-phosphate < 2.0 mg/dL) from baseline to day 35
- Proportion of hypophosphatemia at day 35
- Absolute [Δ] and relative [%] changes in *s*-phosphate from baseline to day 1, 7, 8, 14, 21, and 35
- Fractional phosphate urinary excretion at day 1, 7, 8, 14, 21, and 35
- Change in iFGF23, cFGF23, vitamin D (25, 1.25, 24.25), PTH, and ionized calcium from baseline to day 1, 7, 8, 14, 21, and 35
- Type and incidence of AEs
- Serious or severe hypersensitivity reaction starting on or after the first dose of randomized treatment (i.e. treatment emergent). The hypersensitivity terms are defined as standardised Medical Dictionary for Regulatory Activities query (SMQ) terms (including four additional terms) in the protocol in Appendix A.

Sponsor:	Pharmacosmos A/S	Date:	12MAR2018
Drug/Project:	Monofer	Version:	Final 2.0
Trials:	P-Monofer-IDA-04 P-Monofer-IDA-05		Statistical Analysis Plan

### 7.2.1 Incidence of s-phosphate < 1.0 mg/dL at any time from baseline to day 35

The incidence of s-phosphate < 1.0 mg/dL at any time from baseline to day 35 will be analysed and presented like the primary endpoint using CMH as described in section 5.1.1 and the sensitivity analyses described in section 7.1.1.

The number and percentage of subjects with s-phosphate < 1.0 mg/dL will be summarised by treatment and day. The s-phosphate data will be listed by subject as mentioned in section 7.1.1.

### 7.2.2 Time with hypophosphatemia from baseline to day 35

The time with s-hypophosphatemia will be calculated as the actual number of days from the first day where s-phosphate < 2 mg/dL until the first day where s-phosphate ≥ 2 mg/dL. If the subject does not reach s-phosphate ≥ 2 mg/dL then it will be treated as censored at day 35. If a subject experiences more than one period with s-phosphate < 2 mg/dL, the longest period will be used in the analysis.

The time with hypophosphatemia from baseline to day 35 will be presented by a Kaplan-Meier plot. The treatment groups will be compared by a log-rank test. Only subjects who have one or more s-phosphate value(s) < 2 mg/dL will be included.

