Plots including the Kaplan-Meier curves, log-rank test and median time with hypophosphatemia will be presented overall by treatment. All periods will be presented by subject in a swimmer plot.

### 7.2.3 Proportion of hypophosphatemia at day 35

The proportion of subjects with hypophosphatemia at day 35 will be analysed and presented like the primary endpoint using the CMH described in section 5.1.1. for observed cases only.

The number and percentage of subjects with hypophosphatemia will be summarised by treatment and listed by subject as described in section 7.1.1.

### 7.2.4 Absolute [Δ] and relative [%] changes in s-phosphate from baseline to day 1, 7, 8, 14, 21, and 35

The change in s-phosphate from baseline to day 1, 7, 8, 14, 21, and 35 will be analysed and presented using the MMRM described in section 5.1.1.

The change in s-phosphate will be summarised by treatment and visit, and mean plot of absolute change over time will be presented.

The percentage change in s-phosphate from baseline to day 1, 7, 8, 14, 21, and 35 will be analysed and presented using the MMRM described in section 5.1.1.

The percentage change in s-phosphate will be summarised by treatment and visit, and mean plot of percentage change over time will be presented.

### 7.2.5 Fractional phosphate urinary excretion at day 1, 7, 8, 14, 21, and 35

The fractional phosphate urinary excretion at day 1, 7, 8, 14, 21, and 35 including change from baseline will be summarised by treatment and visit. All data will be listed by subject.

Sponsor: Pharmacosmos A/S	Date: 12MAR2018	
Drug/Project: Monofer	Version: Final 2.0	
Trials: P-Monofer-IDA-04 P-Monofer-IDA-05	Statistical Analysis Plan	

## 7.2.6 Change in iFGF23, cFGF23, vitamin D (25, 1.25, 24.25), PTH, and ionized calcium from baseline to day 1, 7, 8, 14, 21, and 35

The change in each of the following 7 endpoints

- iFGF23
- cFGF23
- vitamin D (25)
- vitamin D (1.25)
- vitamin D (24.25)
- PTH
- ionized calcium

from baseline to day 1, 7, 8, 14, 21, and 35 will be analysed using the MMRM described in section 5.1.1..

A summary of absolute values and change from baseline by treatment and visit, and mean plots of change over time will be presented for each endpoint. All data will be listed by subject.

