## 7.7 Multiplicity adjustments

These trials are two-armed with one primary endpoint, so no multiplicity exists. For the secondary endpoints, treatment differences, CIs and corresponding p-values are presented, but no adjustment for multiplicity will be done.

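### Time with hypophosphatemia is tested between arms, but SAP 7.2.2 names no treatment difference and no confidence interval

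*SAP*

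**What the plan says.** Section 3.1.2 lists time with hypophosphatemia as secondary safety objective (2), to be compared between the treatments, and section 7.2 lists it as a secondary safety endpoint. Section 7.2.2 measures it from the first s-phosphate value below 2 mg/dL to the first value at or above 2 mg/dL. It takes the longest period if there are several, and censors at day 35 those who do not recover. Only subjects with at least one value below 2 mg/dL are included.

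On the comparison, 7.2.2 says: "The treatment groups will be compared by a log-rank test". On the output: "Plots including the Kaplan-Meier curves, log-rank test and median time with hypophosphatemia will be presented overall by treatment". A swimmer plot shows every period by subject. No hazard ratio, difference in medians or difference in mean duration is named, and no confidence interval is given for any quantity.

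Section 7.7 says: "For the secondary endpoints, treatment differences, CIs and corresponding p-values are presented", without multiplicity adjustment. Section 7.10 repeats the individual-trial analyses in the pooled data with trial added. For this endpoint, section 8 records only the change from a table of periods to the swimmer plot.

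**The concern.** A log-rank test gives a p-value but no size of effect. Two medians without intervals give a rough size but no precision. The Kaplan-Meier curves and swimmer plot display the durations, but neither yields a between-arm estimate with its uncertainty. The objective is to compare how long subjects stay low, and the planned output cannot say how much longer one arm stays low or how well that is known.

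This matters most if the test is not significant, because with few cases such a result is compatible with anything from no difference to a large one. A median also does not exist if its curve never falls to 50 %. Since subjects who do not recover are censored, that is most likely in the arm where hypophosphatemia persists longest.

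**Working it through.** **The SAP's own figure first.** Section 3.3.1 gives "The significance level is set to 5 %, and the power is set to 80" %, and then "Assuming incidences of 15 % for iron isomaltoside and 40 % for ferric carboxymaltose", from which "49 subjects in each treatment group is required to detect a difference between the treatment groups". Sidedness is not stated; two-sided is assumed. With mean proportion 0.275:

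n = [1.96 × √(2 × 0.275 × 0.725) + 0.8416 × √(0.15 × 0.85 + 0.40 × 0.60)]² / 0.25² = 48.9, so 49. The figure reproduces. (A one-sided test would give 39.)

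**Subjects in the duration analysis.** Section 3.3.1 also says: "60 subjects per treatment group will be randomized in both trials".
- Per trial: 60 × 0.15 = 9 and 60 × 0.40 = 24.
- Pooled: 120 × 0.15 = 18 and 120 × 0.40 = 48.

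**Precision of a recovery hazard ratio (HR).** With d₁ and d₂ recoveries, SE(log HR) ≈ √(1/d₁ + 1/d₂). The 95 % interval is the HR divided and multiplied by exp(1.96 × SE).

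| Setting | d₁, d₂ | SE | Factor |
|---|---|---|---|
| One trial, all recover | 9, 24 | 0.391 | 2.15 |
| One trial, 20 % censored | 7.2, 19.2 | 0.437 | 2.35 |
| One trial, 40 % censored | 5.4, 14.4 | 0.505 | 2.69 |
| Pooled, all recover | 18, 48 | 0.276 | 1.72 |

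The SAP gives no recovery rate, so the censored fractions are assumptions that show a range.

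**What a reader would not see.** One trial, 9 v 24 cases, all recovering:
- Observed HR 1.0: interval 0.46 to 2.15, p = 1.0.
- Observed HR 1.5: interval 0.70 to 3.23, p = 0.30.
- Observed HR 2.0: interval 0.93 to 4.30, p = 0.076.

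All three are non-significant, and two of the intervals extend beyond a three-fold difference in recovery rate. The planned output gives the p-value without the interval.

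**Sections side by side.**
- 7.2.1 and 7.2.3 (incidence below 1.0 mg/dL; hypophosphatemia at day 35): the CMH method of 5.1.1 gives a risk difference, 95 % CI and p-value.
- 7.2.4 (change in s-phosphate): the MMRM of 5.1.1 gives mean differences with 95 % CIs and p-values.
- 7.2.2: a between-arm test, but neither method is used and no other estimator is named.

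**The case against.** The strongest objection is that 7.7 is being asked to carry too much. The sentence stands under multiplicity, and its main point is that no adjustment is made. It cannot be a literal output list: fractional phosphate excretion (7.2.5) and hypersensitivity (7.2.8) are only summarised. This stands. A reader might infer that 7.2.2 alone breaks a firm commitment, and the SAP does not support that. What remains is that 7.2.2, unlike 7.2.5 and 7.2.8, makes a formal between-arm comparison and still gives no estimate, while its closest neighbours do.

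Second, persistence is partly quantified elsewhere. Section 7.2.3 gives a risk difference with interval at day 35, and 7.2.4 gives mean differences in phosphate change at each post-baseline visit. This narrows the gap, but neither estimates time spent low. It would also be wrong to read the output as nothing but a p-value and two medians, since the curves and swimmer plot show duration and censoring.

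Third, low power might be read as the defect. At 9 v 24 cases, all recovering, log-rank power is about 43 % for a two-fold difference and 80 % is reached only near three-fold. But the SAP claims no power for this endpoint, and reporting an interval would not change the power. Nor does any section say that a non-significant test will be interpreted as equal duration.

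Fourth, the analysed subjects are selected on a post-randomization outcome and have unequal follow-up after onset. A hazard ratio among them is not a randomized comparison, and an interval could lend it undue authority. This stands and shapes the fix.

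**Conclusion.** The point holds as a gap in the reporting of one formally tested secondary safety endpoint. It does not touch the primary analysis or the sample size. Section 7.2.2 and, through 7.10, the pooled analysis name no between-arm estimate and no confidence interval for time with hypophosphatemia. Section 8 does not declare this as an exception to 7.7.

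The hidden imprecision is a factor of about 2.15 either way per trial and 1.72 pooled. These figures rest on the planning incidences of 15 % and 40 %, 60 treated per arm per trial, recovery of all cases and the usual large-sample approximation. Censoring makes the factor larger. That a median will go unreached is a possibility only, because the SAP gives no recovery rate.

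**What to change.** In 7.2.2, and explicitly in its pooled version under 7.10:

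1. Add 95 % CIs for the two medians, and a recovery hazard ratio with 95 % CI beside the log-rank test. Label both as describing cases only, not as a randomized comparison.
2. Add the treatment difference, with 95 % CI, in mean days with s-phosphate below 2 mg/dL from baseline to day 35 over all safety-set subjects, counting non-cases as 0 days. This avoids selecting subjects on the outcome, so it keeps the randomized groups (as far as the safety set, which is analysed as treated, preserves them), and it exists even when a median is not reached. State how days are counted when there is more than one period, when a subject has not recovered by the last value, and when post-baseline values are missing.

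The cost is some SAP text and a little more analysis of s-phosphate data already being collected, with no change to sample size or visits. The downside is that a wide interval will be visible.

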##### 3.1.2 Secondary safety objectives

The secondary safety objectives of the trials are to compare the effects of iron isomaltoside and ferric carboxymaltose treatment in subjects with IDA on the following:

- (1) Incidence of severe hypophosphatemia
- (2) Time with hypophosphatemia
- (3) Proportion of subjects with hypophosphatemia at the last visit
- (4) Absolute [Δ] and relative [%] changes in serum-phosphate (s-phosphate)
- (5) Fractional phosphate urinary excretion
- (6) Intact Fibroblast Growth Factor 23 (iFGF23), C-terminal FGF23 (cFGF23), vitamin D (25, 1.25, 24.25), Parathyroid Hormone (PTH), and ionized calcium
- (7) Adverse Events (AEs) and biochemical safety parameters

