**Table 2 Visit schedule**

Visit	1 Screening	2 Baseline	3	4	5	6	7	8
Time (days)	Max -28	0	1	7	8	14	21	35
Visit window (days)	-	-	+ 1	+ 1	+ 1	± 2	± 3	± 3

The visits will be labelled by screening, baseline and scheduled day. Categorical data will be summarized by treatment, using number and percentages of subjects. For calculation of percentages, the denominator will either be the number of subjects in the analysis set or the number of subjects in the analysis set with non-missing values. Continuous data will be presented using the number of subjects (n), mean, standard deviation (SD), median, lower quartile, upper quartile, minimum and maximum. Both the absolute values and the change from baseline will be presented.

Sponsor:	Pharmacosmos A/S
Drug/Project:	Monofer
Trials:	P-Monofer-IDA-04 P-Monofer-IDA-05

Date:	12MAR2018
Version:	Final 2.0
Statistical Analysis Plan	

Descriptive statistics for all endpoints will be presented by treatment group and day, if applicable, using observed cases, i.e. no imputation of missing data will be performed. Missing data for time to event endpoints is handled using censoring.

Values below lower limit of quantification (LLOQ) will be substituted by 0.5\*LLOQ in tables and figures.

In the following, strata are defined as *Type of underlying disease: women with IDA due to gynaecological blood losses (yes or no) and screening s-phosphate level (< 3.5 mg/dL or ≥ 3.5 mg/dL)*.

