## 7.2.7 Type and incidence of AEs

AEs will be coded using the Medical Dictionary for Regulatory Activities (MedDRA) current version. AEs will be regarded as treatment emergent AEs (TEAEs) if they either occur after administration of randomised treatment or occur before and are worsened after randomised treatment. Related or possible related AEs are defined as Adverse Drug Reactions (ADRs).

Summary by system organ class (SOC) and preferred term (PT) indicating number and percentage of subjects and number of events will be presented for:

- TEAEs
- Treatment emergent serious adverse events (SAEs)
- TEAEs by severity (mild, moderate, severe)
- TEAEs by relationship (related, possible, unlikely, not related, unknown)

An overall summary table by treatment will present number of events, number of subjects, and proportion of subjects reporting Non-TEAEs, TEAEs, Treatment emergent SAEs, Fatal SAEs, ADRs, Suspected Unexpected Serious Adverse Reaction (SUSARs), TEAEs by severity, and TEAEs by outcome. Number of subjects who experience an ADR including SUSARs will be compared between treatment groups using Fisher's Exact test.

Non-treatment emergent SAEs for subjects who never received trial drug will be listed.

The following lists will be made for the safety analysis set:

- Non-treatment emergent AEs and SAEs
- TEAEs
- Treatment emergent SAEs
- ADRs
- AEs leading to dose reduction or withdrawal from treatment
- Fatal SAEs

Sponsor: Pharmacosmos A/S  
Drug/Project: Monofer  
Trials: P-Monofer-IDA-04  
P-Monofer-IDA-05

Date: 12MAR2018  
Version: Final 2.0  
Statistical Analysis Plan

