## 7.2.8 Serious or severe hypersensitivity reaction

The hypersensitivity reactions are defined by the SMQs but including four additional terms, see the protocol Appendix A.

The number of events, number of subjects, and proportion of subjects reporting serious or severe hypersensitivity reaction starting on or after the first dose of randomized treatment will be summarised by SMQ and PT. Serious or severe hypersensitivity reactions will be listed.

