## 7.10 Combined Analysis of P-Monofer-IDA-04 and P-Monofer-IDA-05

The two trials P-Monofer-IDA-04 and P-Monofer-IDA-05 is planned to run in parallel and the same dosing regimens are investigated.

Pooled analyses of primary and secondary safety and efficacy endpoints will be performed for the two trials.

The analyses will be performed similar to those specified for the individual trials, with the addition of trial in the models, i.e. the CMH method will be stratified by strata and trial and the MMRM will include the fixed, categorical effects of trial, treatment, strata, day, treatment-by-day interaction. Also, the overall incidence of TEAEs and ADRs will be compared between the treatment groups using Fisher's Exact test.

The CSRs will be finalised without the combined analyses, which will be done when both trials are finalised. The combined analysis will be included as an appendix to the CSRs.

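### Fractional phosphate urinary excretion is a comparative secondary objective, but SAP 7.2.5 specifies only by-arm summaries, so no between-arm estimate, interval or test is pre-specified

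*SAP*

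**What the plan says.** Section 3.1.2 opens: "The secondary safety objectives of the trials are to compare the effects of iron isomaltoside and ferric carboxymaltose treatment". Fractional phosphate urinary excretion is item (5), and 7.2 lists it as a secondary safety endpoint at six post-baseline days.

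The analysis in 7.2.5 is that "fractional phosphate urinary excretion at day 1, 7, 8, 14, 21, and 35 including change from baseline will be summarised by treatment and visit", followed by a by-subject listing. It names no model, difference, interval or test.

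Section 7.7 says: "For the secondary endpoints, treatment differences, CIs and corresponding p-values are presented, but no adjustment for multiplicity will be done".

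For the combined analysis, 7.10 says: "The analyses will be performed similar to those specified for the individual trials, with the addition of trial in the models".

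**The concern.** An objective worded as a comparison is paired with an analysis section that contains none, while 7.7 implies that one will be reported. The sections on either side, 7.2.4 and 7.2.6, both assign the MMRM of 5.1.1. So does every exploratory endpoint in 7.5.1 to 7.5.8. A named secondary objective therefore gets less inference than endpoints that the SAP calls purely exploratory, and no reason is given.

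If the plan is followed as written, the CSR reports objective (5) without a pre-specified estimate of the treatment difference. If a model is added later, section 2 requires it to be specified in the CSR as a deviation. In an open-label trial, the scale (value or change), covariates and days would then be chosen after the data exist.

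**Working it through.** **1. Is a comparison specified elsewhere?**

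- 5.1 adds descriptive statistics only: "Both the absolute values and the change from baseline will be presented".
- 5.1.1 offers CMH and MMRM for several endpoints, so neither is a default.
- 7.7 names no estimator, scale or day for this endpoint.
- 7.10 repeats the individual-trial analyses with trial added. With no model in 7.2.5, there is none to extend.
- Section 8 does not mention this endpoint.

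**2. Continuous secondary endpoints at the six visits**

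- 7.2.4: 2 (absolute and percentage change in s-phosphate)
- 7.2.5: 1
- 7.2.6: 7
- 7.3.1 to 7.3.3: 3 (Hb per gram iron counted once)

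The total is 2 + 1 + 7 + 3 = 13. Twelve have the MMRM and 7.2.5 does not. The biochemical safety parameters of objective (7), reported descriptively in 7.4.3, are outside this count.

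**3. How far the 7.7 sentence holds**

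There are 8 safety and 3 efficacy endpoint sections, 11 in all. A difference with CI and p-value is specified in seven: 7.2.1, 7.2.3, 7.2.4, 7.2.6, 7.3.1, 7.3.2 and 7.3.3. It is not specified in four:

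- 7.2.2: "The treatment groups will be compared by a log-rank test", with median times
- 7.2.5: summary only
- 7.2.7: "Number of subjects who experience an ADR including SUSARs will be compared between treatment groups using Fisher's Exact test", otherwise descriptive
- 7.2.8: events "will be summarised by SMQ and PT. Serious or severe hypersensitivity reactions will be listed"

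Adding the MMRM to 7.2.5 would make it 8 of 11.

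**4. The plan's sample size**

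The point does not depend on this figure, but it supplies n. With 15% against 40%, two-sided 5% and 80% power (pooled variance, no continuity correction):

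n = [1.96·√(2·0.275·0.725) + 0.842·√(0.15·0.85 + 0.40·0.60)]² / 0.25² ≈ 49 per group.

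This reproduces the SAP. It randomizes 60 per group in each trial, hence 120 per group pooled.

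**5. What a reader loses by using the summaries**

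Assumptions: SD = 1 at baseline and follow-up; baseline to follow-up correlation r is not in the document and is taken as 0.3, 0.5 or 0.7; complete data at a single visit; strata ignored. The adjusted formula approximates the MMRM contrast. The 95% CI half-widths, in SD units, are:

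- Follow-up means: t(0.975, 2n−2)·√(2/n)
- Change: the same × √(2(1−r))
- Baseline-adjusted: t(0.975, 2n−3)·√(2/n)·√(1−r²)

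| n per arm | r | Follow-up | Change | Adjusted | Better summary ÷ adjusted |
|---|---|---|---|---|---|
| 60 | 0.3 | 0.362 | 0.428 | 0.345 | 1.048 |
| 60 | 0.5 | 0.362 | 0.362 | 0.313 | 1.155 |
| 60 | 0.7 | 0.362 | 0.280 | 0.258 | 1.085 |
| 120 | 0.3 | 0.254 | 0.301 | 0.243 | 1.048 |
| 120 | 0.5 | 0.254 | 0.254 | 0.220 | 1.155 |
| 120 | 0.7 | 0.254 | 0.197 | 0.182 | 1.085 |

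**6. Added multiplicity**

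12 × 6 = 72 visit contrasts per trial become 13 × 6 = 78, an increase of 6/72 = 8.3%.

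**The case against.** The best defence is that a comparative objective need not mean a test. The same opening words in 3.1.2 govern objective (7), adverse events and biochemical safety parameters, and these are handled almost entirely by description. The endpoint is also listed as a value at each day, whereas the MMRM is defined for change from baseline, so a descriptive treatment may be deliberate. Section 8 lists no deviation here, which would fit a protocol that is also descriptive. Section 7.7 is a multiplicity statement and can be read as saying only that whatever p-values are presented are unadjusted. Finally, by-arm n, mean and SD will be reported, so an unadjusted difference can be calculated.

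Parts of this stand. The word used in 3.1.2 does not by itself force a model, descriptive intent cannot be excluded without the protocol, and the practical consequence is modest. But none of it supplies a between-arm comparison for this endpoint. Section 7.2.5 already summarises change from baseline, so the listing as a value does not explain the absence of the MMRM. A descriptive protocol would not remove the mismatch between this SAP's own 3.1.2, 7.2.5 and 7.7.

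**Conclusion.** The concern holds. One of 13 continuous secondary endpoints at these visits has no pre-specified difference, interval or test, in either trial or pooled, although comparing the arms on it is a stated objective. The pooled gap is the same defect carried forward, not a second one.

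This rests on the text and the counts. The 5% to 15% loss of precision depends on the assumed correlations and is supporting context only. A side-by-side descriptive reading remains possible. The change should be made because it is cheap and lets the trials answer objective (5).

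**What to change.** - **7.2.5:** state that change from baseline to days 1, 7, 8, 14, 21 and 35 is analysed with the MMRM of 5.1.1, reporting treatment differences, 95% CIs and p-values.
- **7.10:** the same model then applies with trial added.
- **Section 8:** add an entry if the protocol is descriptive only for this endpoint.
- **7.7:** restrict the sentence to endpoints for which a comparison is specified, noting that 7.2.2, 7.2.7 and 7.2.8 do not provide a difference with CI.

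If the endpoint is intended to be descriptive, say so in 3.1.2 and 7.7 instead. That would align the text but leave objective (5) without an inferential answer.

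The cost is one sentence in 7.2.5, one clause in 7.7, possibly a section 8 entry, and one more run of an existing program per trial and pooled. Urine is already sampled at baseline and all six post-baseline visits (Table 1). The downside is six more unadjusted contrasts per trial.
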